5.2.6 Relapsed and/or Refractory Multiple Myeloma

Study C16004 is an open-label, dose-escalation, phase 1 study of MLN9708 administered weekly on Days 1, 8, and 15 of a 28-day cycle in adult patients with RRMM. Patients with MM enrolled in the dose-escalation component of the study have relapsed following at least 2 lines of therapy, which must have included bortezomib, thalidomide (or lenalidomide), and corticosteroids. The dose-escalation phase of the trial has completed. In this study, 2 of 3 patients experienced protocol-defined DLTs (Grade 3 rash and Grade 3 nausea, vomiting, and diarrhea) at a dose of 3.95 mg/m2. As per protocol, subsequent patients were treated at 1 dose level below (2.97mg/m²) where 1 of 6 patients experienced a DLT (Grade 3 nausea, vomiting, and diarrhea). The MTD of weekly oral MLN9708 was determined to be 2.97 mg/m².

Once the MTD was established, cohorts of patients representing the heterogeneous patient population currently seen in clinical practice were enrolled in order to further evaluate the safety,

tolerability, efficacy, PK, and pharmacodynamics of oral MLN9708. The MTD expansion cohorts enrolling are:

- 1. Relapsed and Refractory expansion cohort [refractory is defined as disease progression while on therapy or within 60 days after the last dose of therapy];
- 2. Carfilzomib expansion cohort
- 3. Proteasome Inhibitor-Naïve expansion cohort
- 4. VELCADE-Relapsed expansion cohort

Final study results are not available for this ongoing trial, but preliminary data suggest MLN9708 has antitumor activity in heavily pretreated MM patients, with durable responses/disease control, and is generally well tolerated.^{20 21}

As of the 30 April 2012 data cut, these patients are considered heavily pretreated as evidenced by a median number of 4 (range 1–13) prior lines of therapy, with 66% refractory to the last line of therapy. Patients have received a median of 2 cycles of therapy (range, 1- 11). Five patients have achieved objective response: 1 patient achieved a VGPR and 4 patients achieved a PR. Additionally, 15 patients achieved durable disease stabilization for up to 9.5 months. At data cut-off, 15 patients remain on treatment; discontinuation of treatment was primarily due to progressive disease (69%).

A summary of the safety profile of patients treated in Study C16004 is outlined in Table 5-4. Overall, 92% of patients experienced a TEAE of any grade and of any cause. Peripheral neuropathy was limited to Grade 1/2 in 6 patients, with 3 patients reporting baseline Grade 1 PN at study entry.

Table 5-4 Study C16004, Oral MLN9708, Single Agent, Given Weekly: Most Common TEAEs as of 30 April 12 (N= 52)

Thrombocytopenia (54%)
Fatigue (48%)
Nausea (44%), diarrhea (44%)
Vomiting (37%)
Decreased appetite (33%)
Rash* (31%)
Anemia (25%)
Neutropenia (23%)
Thrombocytopenia (38%)
Diarrhea and neutropenia 17% (each), fatigue and
lymphopenia 10% (each), nausea and decreased
appetite 8% (each) and vomiting 6%

Source: MLN9708 Investigator's Brochure Edition 6

^{*} Rash includes preferred terms of rash macular, rash, maculo-papular, rash morbilliform, rash pruritic, pruritus,, rash erythematous, exfoliative rash, and rash popular

Dose reductions required were due to AEs that included rash, neutropenia, thrombocytopenia, diarrhea, nausea, vomiting, dehydration, hypotension, increase in serum creatinine, abdominal pain, ileus, fatigue, and pneumonia. The AEs reported for the 5 patients who were required to discontinue treatment included Grade 2 MLN9708-related nausea/vomiting in 1 patient treated above the MTD, Grade 3 MLN9708-related diarrhea in a second patient, related Grade 3 thrombocytopenia, related Grade 2 dyspnea, and not related Grade 4 elevation in creatinine (1 patient each). There were no onstudy deaths.

Study C16007 is evaluating single agent weekly, Day 1, 8, and 15 of a 28-day cycle, oral dosing in patients with RRAL after at least 1 prior therapy. The objectives of this study are to determine the safety, tolerability, and MTD, as well as to determine hematologic and organ response rates in this patient population. The starting dose level was selected from Study C16004 as previously described. In Study C16007 the dose was switched from the BSA-based dosing to the fixed dose, thereby the 4.0 mg fixed starting dose in Study C16007 corresponds to the 2.23 mg/m2 dose (one dose level below MTD) from Study C16004. This study is currently enrolling patients in the dose-expansion portion of the trial.

As of 30 April 2012, 14 patients have been treated in this study. At the first dose level of 4.0 mg, 1 of 6 patients experienced a protocol-defined DLT (that is, thrombocytopenia that lasted more than 2 weeks, which met the definition of a DLT due to the delay in starting Cycle 2). As per protocol, the dose was escalated to 5.5 mg for the next cohort of patients where 2 of 5 patients experienced a DLT (Grade 3 diarrhea, n=1; and Grade 2 dyspnea, Grade 2 acute rise in serum creatinine, and Grade 4 cardiac arrest, n=1). The latter patient did not appear to have cardiac AL amyloidosis by echocardiogram on study entry, but did have substantial renal involvement. After the occurrence of this DLT, diagnoses included cardiac involvement and CHF. The MTD of weekly oral MLN9708 was determined to be 4.0 mg. Following the establishment of the MTD, patients are currently being enrolled in to 1 of 2 cohorts: proteasome inhibitor naïve or proteasome inhibitor exposed. As of the 30 April 2012 data cut, the patients enrolled in the study are considered heavily pretreated, as evidenced by a median number of 3 prior lines of therapy (range 1-7), with 38% and 46% of patients having been previously treated with bortezomib and lenalidomide, respectively. To be eligible for the study, patients must have amyloid involvement of the heart, kidney, or both; at the data cut the organ involvement distribution was 6, 4, and 4 patients, respectively. Patients have received a median of 2.5 cycles of therapy (range, 1-12). Eight patients remain on treatment. Early signs of activity have been reported. There were 11 patients who have received at least 1 cycle of therapy with completed response assessments (9 in the 4.0 mg [MTD] cohort and 2 in the 5.5 mg cohort). The overall hematologic response rate at MTD is 56% (5 patients achieved a hematologic response [4 VGPR and 1 PR]; 3 patients showed no change, and 1 patient had an early progression.

A summary of the safety profile of patients treated in Study C16007 is outlined in Table 5-5. Overall, 86% of patients experienced a TEAE of any grade and of any cause.

Table 5-5 Study C16007, Oral MLN9708, Single Agent Given Weekly Most Common TEAEs as of 30April 12 (N = 14)

43 01 30April 12 (11 = 14)	
Most Common (> 20%)	Nausea (50%)
Any Grade and Irrespective of Cause	Fatigue (36%)
	Thrombocytopenia (29%)
	Diarrhea (29%)
	Decreased Appetite (21%)
	Peripheral Edema (21%)
	Dyspnea (21%)
	Abdominal pain (21%)
Drug-Related Grade ≥ 3 in more than 3 Patients	Thrombocytopenia 5 patients, rash 3 patients,
-	dehydration 2 patients, fatigue 2 patients

Source: MLN9708 Investigator's Brochure Edition 6

One patient discontinued study drug administration due to a TEAE (patient with DLT of acute rise in serum creatinine, dyspnea, and cardiac arrest treated at 5.5 mg, as noted above). No death has been reported.

The potential risks reported with MLN9708 use, pooled from all studies using the oral formulations, were anticipated based on preclinical data and previous experience with VELCADE and are noted in the MLN9708 IB, SMA, and ICF documents. Regardless of whether MLN9708 is administered on the once weekly or twice weekly dosing schedule, there is consistency among the type of TEAEs reported, despite some differences in the frequency and severity of the reported events. While the predominant potential toxicities may be severe in some cases, they are largely reversible, and can be managed by routine clinical monitoring and standard medical interventions, which may include dose reductions and supportive care. Please refer to the MLN9708 IB and SMA for further information.

5.2.7 Newly Diagnosed Multiple Myeloma (NDMM)

In Study C16005, MLN9708 is given weekly (Days 1, 8, and 15), in combination with lenalidomide (Days 1-21), and dexamethasone (Days 1, 8, 15, and 22) in a 28-day cycle. Enrollment to this study is closed.

Clinical data as of 30 April 2012 is available. The MTD in Study C16005 was determined to be 2.97 mg/m² given weekly in a 28-day cycle with LenDex. The DLTs were urticarial rash, dizziness, nausea, orthostatic hypotension, vomiting, diarrhoea, and syncope. The recommended phase 2 dose (RP2D) estimation was established following evaluation of the available data from the phase 1 portion of the trial which included, but was not limited to, analyses of efficacy results and adverse events (Grade 3/4 AEs, SAEs, all grades peripheral neuropathy, and treatment discontinuation). Given that the dose of MLN9708 at 2.97 mg/m² compromised the maximal dosing of lenalidomide and that the dose of 2.23 mg/m² is very tolerable and clinically active, Millennium designated 2.23 mg/m² as the RP2D after evaluation of the data and discussion with investigators. The RP2D of 2.23 mg/m² has been

translated into a fixed dose of 4.0 mg based on the results from the population PK analysis. Enrollment in this study has been completed; final study results are not available, but preliminary data suggests oral MLN9708 given weekly plus lenalidomide and dexamethasone in a 28-day cycle appears well tolerated with manageable toxicity and encouraging antitumor activity.

In Study C16005, 15 of 15 (100%) patients in the dose escalation portion of the study experienced at least 1 TEAE irrespective of grade or causality. At the MTD across all dose expansion cohorts 49 of 53 patients (including 3 patients from the dose escalation cohort [92%]) reported at least 1 TEAE irrespective of grade or causality. In the MTD cohorts, fatigue was the most common AE reported (38%). Other common AEs reported include nausea (32%), constipation (30%), upper respiratory infection (23%), and peripheral oedema (21%). Skin toxicity, primarily erythematous rash, occurred in 62% of patients (of note, rash is an overlapping toxicity with MLN9708 and lenalidomide). Peripheral neuropathy was reported in 13% of patients; Grade 3 in 1 patient.

A summary of the overall safety profile of patients treated in Study C16005 is outlined in Table 5-6. Overall, 100% of 65 patients experienced at least one TEAE of any grade and of any cause.

Table 5-6 Study C16005: Oral MLN9708 Given Weekly in Combination With Lenalidomide and Dexamethasone, Most Common TEAEs as of 30 April 2012

and Dexamethasone, Most Common TEAEs as of 30 April 2012			
Most Common (> 20%) Any Grade and Irrespective	Fatigue (37%)		
of Cause	Nausea (34%)		
	Constipation (31%)		
	Vomiting (28%)		
	Diarrhoea (26%)		
	Thrombocytopenia (23%)		
	Upper respiratory tract infection (22%)		
	Anaemia and oedema peripheral (20% each)		
Drug-Related ^a Grade ≥ 3 in ≥ 2 Patients	Nausea, vomiting (n=3 each)		
	Thrombocytopenia, lymphopenia, rash pruritic (n=2 each)		

Source: MLN9708 Investigator's Brochure Edition 6.

a Related means to ANY drug in the study drug combination.

The most common drug-related SAEs reported in Study C16005 as of 30 April 2012 include pneumonia, infection, diverticulitis, localised infection, gastrointestinal haemorrhage, respiratory syncytial virus (RSV) pneumonia faecaloma, pyrexia, pneumonia respiratory syncytial viral, non-cardiac chest pain, peripheral oedma, asthenia, hyponatraemia vomiting, diarrhoea, nausea, chest pain, dehydration, anemia, dizziness, peripheral sensory neuropathy, orthostatic hypotension, embolism, muscular weakness, acute renal failure, blood creatinine increased, maculopapular rash, atrial fibrillation, syncope, hypotension, and deep vein thrombosis, and back pain.

As of the clinical data cutoff, 4 patients have discontinued treatment due to TEAEs including

gastrointestinal haemorrhage, angioedema, syncope, and RSV pneumonia.

One death was reported for a patient with RSV pneumonia; the event was deemed by the investigator to be related to treatment with MLN9708.

5.3 Rationale of the study

In view of the considerations described in the introduction, a triple combination induction regimen with an oral PI, an IMiD and a corticosteroid preferably should be oral and with a low risk for the development of painful neuropathy. In addition, the costs of therapy should be taken into account. These requirements are met by a triple combination induction therapy with ixazomib citrate as a proteasome inhibitor, thalidomide as an IMiD and low dose dexamethasone. Besides an effective induction regimen, especially in the elderly in whom induction therapy might be less dose intense and of shorter duration due to toxicity, the role of maintenance therapy has to be defined.²² Thalidomide maintenance has shown not to be effective given a limited improvement in PFS only, without improving OS in the elderly population. 10 Although lenalidomide has been shown to considerably increase PFS, improvement in OS has to be shown yet in 2 out of 3 studies. Moreover, the increased incidence of SPM is a concern during maintenance. 1 2 3 4 The non head-to-head comparison of maintenance with VP or VT following MPV or MPT with the classical VISTA without maintenance suggest a role for maintenance therapy with a PI.59 Therefore, we aim to assess the efficacy and feasibility of this triple combination induction therapy with Ixazomib as a PI, Thalidomide as an IMiD and low dose Dexamethasone. Moreover, the merits and feasibility of MLN9708 (Ixazomib) maintenance will be determined. The data from this study may allow to design a future randomized phase III clinical trial comparing ixazomib citrate-thalidomide-low dose dexmethasone either with or without maintenance therapy with ixazomib citrate with an alkylating based regimen.

6 Study objectives

In newly diagnosed patients with MM who are not eligible for ASCT:

Primary objectives

Maintenance treatment

◆ To compare progression free survival between maintenance therapy with Ixazomib versus placebo, both following induction therapy with ixazomib citrate – thalidomide – low dose dexamethasone

Induction treatment

- ◆ To determine overall response* rate of induction therapy with ixazomib citrate thalidomide
 - low dose dexamethasone
 - * overall response will be defined as (stringent) complete response, very good partial response and partial response (appendix C)

Secondary objectives

- To determine toxicity, polyneuropathy in specific, during induction treatment and maintenance treatment with ixazomib citrate or placebo
- ♦ To determine progression free survival and overall survival from registration
- ♦ To compare the efficacy between maintenance treatment with ixazomib citrate versus placebo determined as overall survival from randomization
- To determine the efficacy of maintenance therapy determined as an improvement in response during maintenance treatment with ixazomib citrate or placebo
- ♦ To determine efficacy of induction therapy determined as time to response
- ♦ To determine feasibility, defined as discontinuation rate due to toxicity, during induction treatment and maintenance treatment with ixazomib citrate or placebo
- To determine time to next treatment
- To determine PFS on second line therapy
- To determine Quality of Life during induction treatment and maintenance therapy with Ixazomib or placebo
- To identify clinical, imaging-related and molecular markers prognostic and predictive for outcome and toxicity
- To establish second primary malignancies (SPM)

7 Study design

This is a multicenter phase II clinical trial, with upfront registration and late double-blind, placebocontrolled, maintenance randomization. Details of all treatments (dose and schedule) are given in section 9 and appendix F, G and H.

- 1. Patients will be registered, and then they will be treated with 9 cycles of induction therapy* with ixazomib citrate— thalidomide low dose dexamethasone;
- 2. After induction, patients eligible for randomization will be randomized double-blind between maintenance treatment with ixazomib citrate versus placebo.

The primary objective of this trial is to assess whether maintenance with ixazomib citrate improves PFS (calculated from date of randomization) as compared to placebo. This is used for the sample size calculation. This trial is therefore a superiority trial.

* Randomization and subsequent start of maintenance therapy is allowed after a minimum of 6 induction cycles as described in 8.2.1.

8 Study population

All eligible patients have to be registered before start of treatment. After the induction treatment patients will be randomized.

8.1 Eligibility for registration

All patients must meet all of the following eligibility criteria.

8.1.1 Inclusion criteria

- Previously untreated patients with a confirmed diagnosis of symptomatic multiple myeloma according to IMWG criteria (see appendix A)
- Measurable disease according to the IMWG criteria (see appendix A)
 (If plasmacytoma is the only measurable parameter, the patient is not allowed to be included in the study, because of difficult response evaluation)
- Age ≥ 66 years or patients ≤ 65 years not eligible for ASCT
- WHO performance status 0-3 for patients <75 years and WHO performance status 0-2 for patients ≥ 75 years (see appendix D)
- Absolute neutrophil count (ANC) ≥ 1.0 x10⁹/l and platelet count ≥ 75x10⁹/l, unless related to bone marrow infiltration by malignant plasmacells
 Platelet transfusions to help patients meet eligibility criteria are not allowed within 3 days before study enrollment
- Written informed consent
- Patient gives consent for extra bone marrow and blood sampling
- Negative pregnancy test at study entry or at least 1 year post-menopausal or surgically sterile before study entry
- ◆ A female patient of childbearing potential, agrees to practice 2 effective methods of contraception, at the same time, from the time of signing the informed consent through 90 days after the last dose of study drug, AND must also adhere to the guidelines of any treatment-specific pregnancy prevention program (for thalidomide) OR agrees to completely abstain from heterosexual intercourse. (Periodic abstinence (eg, calendar, ovulation, symptothermal, post-ovulation methods) and withdrawal are not acceptable methods of contraception)

♦ Male patients, even if surgically sterilized, (i.e., status post vasectomy) must agree to practice effective barrier contraception during the entire study period and through 90 days after the last dose of study drug, AND must also adhere to the guidelines of any treatment-specific pregnancy prevention program (for thalidomide), OR agrees to completely abstain from heterosexual intercourse (Periodic abstinence (eg, calendar, ovulation, symptothermal, post-ovulation methods] and withdrawal are not acceptable methods of contraception).

8.1.2 Exclusion criteria

- Known allergy to any of the study medications, their analogues, or excipients in the various formulations of any agent
- Systemic AL amyloidosis
- Polyneuropathy, grade 3 or higher or grade 2 with pain on clinical examination during the screening period
- ♦ Evidence of current uncontrolled cardiovascular conditions, including uncontrolled hypertension, uncontrolled cardiac arrhythmias, symptomatic congestive heart failure, unstable angina, or myocardial infarction within the past 6 months
- Severe pulmonary dysfunction (Modified Medical Research Counsil dyspnea scale classification III-IV)
- Significant hepatic dysfunction (total bilirubin ≥ 1.5 x ULN or transaminases ≥ 3 times normal level) except patients with Gilbert's syndrome as defined by > 80% unconjugated bilirubin
- ♦ Creatinine clearance <30 ml/min or Calculated Glomerular Filtration Rate [ml/min/1.73m²] <30.
- ♦ Systemic treatment, within 14 days before the first dose of ixazomib, with strong CYP3A inducers (rifampin, rifapentine, rifabutin, carbamazepine, phenytoin, phenobarbital), or use of Ginkgo biloba or St. John's wort.Pre-treatment with cytostatic drug, IMIDs or proteasome inhibitors. Radiotherapy or a short course of steroids (e.g. 4 day treatment of dexamethasone 40 mg/day or equivalent) are allowed. Radiotherapy should not be given within 14 days before enrollment. In case of palliative radiotherapy for pain control and if the involved field is small, 7 days will be considered a sufficient interval between treatment and administration of the ixazomib citrate
- ♦ Not able and/or not willing to use adequate contraception
- Female patients who are lactating or have a positive serum pregnancy test during the screening period
- Major surgery within 14 days before enrollment
- Central nervous system involvement
- Ongoing or active systemic infection, active hepatitis B or C virus infection, or known human immunodeficiency virus (HIV) positive

- Known GI disease or GI procedure that could interfere with the oral absorption or tolerance of ixazomib citrate including difficulty swallowing
- Diagnosed or treated for another malignancy within 2 years before study enrollment or
 previously diagnosed with another malignancy and have any evidence of residual disease.
 Patients with nonmelanoma skin cancer or carcinoma in situ of any type are not excluded if
 they have undergone complete resection
- Participation in other clinical trials, including those with other investigational agents not included in this trial, within 21 days of the start of this trial and throughout the duration of this trial
- Any serious medical or psychiatric illness, or familial, sociological and geographical condition potentially hampering compliance with the study protocol and follow-up schedule

8.2 Randomization after induction treatment.

Patients should be randomized and start maintenance treatment after induction treatment, at least 12 weeks after the start of the last cycle.

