9.1 Induction treatment with ixazomib citrate/thalidomide/low dose dexamethasone

9.1.1 Treatment schedule

Induction therapy should start within 4 weeks after patient registration. Patients will receive 9 cycles of ixazomib citrate (4 mg) on days 1, 8, 15 of a 28-day cycle and a daily dose of thalidomide (100 mg) continuously plus dexamethasone (40 mg) on days 1, 8, 15 and 22.

Agent	Dose/day	Route of administration	Days
Ixazomib citrate	4 mg	p.o	1,8 and 15
Thalidomide	100 mg	p.o	1 - 28
Dexamethasone	40 mg	p.o.	1, 8, 15 and 22

After cycle 1, 3, 5, 7 and 9 evaluation will take place. In case of progressive disease after cycle 3, 5, 7 or 9 patients will go off protocol treatment.

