9.2 Maintenance treatment with ixazomib citrate or Placebo maintenance

9.2.1 Treatment schedule

After the response evaluation of the last ixazomib citrate -thalidomide-low dose dexamethasone cycle patients will be randomized. In randomized patients, maintenance treatment with either ixazomib citrate or placebo will be started within a maximum of 12 weeks after start of the last ixazomib citrate - thalidomide-low dose dexamethasone cycle, at a dose of 4 mg on days 1, 8, and 15 of a 28-day cycle.

Maintenance cycles will be repeated at 28-days intervals until progression or when a medical condition occurs that requires discontinuation of the treatment.

Agent	Dose/day	Route	Days
Ixazomib citrate or	4 mg*	p.o	1, 8 and 15
placebo			

^{*}or at the dose level during induction therapy in case dose reductions were required during induction therapy

Response evaluation will take place as described in chapter 10.

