days of the expected date, a reminder/request will be sent to the local QoL coordinator to collect and send in the questionnaire.

NMSG participants

The patients are registered at the HOVON data center. If the patient has signed the consent to participate in the QoL study, he/she will be asked to fill in the baseline questionnaire which is sent to QoL center at Ullevål Hospital, Oslo. All centers will be provided with questionnaires and prestamped reply envelopes. When the first questionnaire is received at the QoL center, new questionnaires with prestamped envelopes will be sent out at regular intervals. The procedure in the Dutch and NMSG branch is similar except that Ullevål Hospital will be the Nordic QoL center.

Quality of life will be measured:

- at entry
- after cycle 3
- after cycle 6
- after cycle 9 or earlier in case of premature discontinuation of induction treatment
- at 6 months after start of maintenance therapy
- at 12 months after start of maintenance therapy
- at discontinuation of maintenance therapy

The quality of life measurements will be stopped when patient goes off protocol treatment.

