14.2.1 Efficacy analysis

The main endpoint will be PFS from the date of randomization. The formal test for difference in PFS between the two treatment arms will be done with a multivariate Cox regression analysis with adjustment for International Scoring System (ISS, I vs II and III), age (<75 vs ≥ 75 years) and response after induction treatment ((s)CR vs VGPR and PR). An estimate of the HR with corresponding 95% CI will be obtained. The actuarial Kaplan-Meier method will be used to estimate PFS probabilities at appropriate time points, while the Greenwood estimate will be used to construct corresponding 95% CIs. Competing risk analysis will be used to calculate cumulative incidences of PFS, progression/relapse, and death without progression (which add up to 100% at every time point). A Kaplan-Meier curve will be generated to illustrate PFS in each arm. In case the accrual will be 18 months, randomization will take place 9 months after registration of the last patient, and if 12 months of follow up after the last patient is required, then the final analysis may be performed after 18 + 9 + 12 = 39 months after start of the trial, if the complete and validated data including 55 events are available. The response rate after induction chemotherapy will be summarized as the proportion of patients with at least a PR, together with a 95% CI.

A preliminary efficacy analysis on response after induction treatment is planned when the data regarding induction treatment and response of the first 50 registered and eligible patients are available and have been evaluated. No conclusions will be drawn based on this analysis.

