14.4 Statistical analysis of the quality of life assessement

All patients with the baseline and at least one follow-up QoL questionnaire, separately for QLQ-C30 and QLQ-MY20, will be included in the analysis, The main purpose will be to describe QoL during induction chemotherapy and maintenance or placebo. QoL after randomization will also be summarized separately for both randomized groups. For randomized patients, the QoL after the last induction chemotherapy will then be considered as baseline. To evaluate the difference in QoL between the two randomization arms with respect to the multi-item scales of the QLQ-C30 and QLQ-MY20, the repeated measures may be analyzed separately using mixed ANOVA models, and the single items using (ordinal) logistic regression with random effects. However, the limited number of randomized patients implies limited power, which might hamper firm conclusions.

15 Registration and Randomization

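### Section 8.2 sets 12 weeks after the start of the last induction cycle as the earliest point for randomisation and start of maintenance, Section 9.2.1 sets it as the latest start; Section 8.2 should be corrected.

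*Protocol*

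**What the plan says.** Section 8.2, which opens the rules for randomisation, states: "Patients should be randomized and start maintenance treatment after induction treatment, at least 12 weeks after the start of the last cycle".

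Section 9.2.1, the maintenance treatment schedule, gives the order of events, "After the response evaluation of the last ixazomib citrate -thalidomide-low dose dexamethasone cycle patients will be randomized", and then says that maintenance "will be started within a maximum of 12 weeks after start of the last" induction cycle.

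Other parts of the protocol bear on the same interval:

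- Section 7 (footnote): "Randomization and subsequent start of maintenance therapy is allowed after a minimum of 6 induction cycles as described in 8.2.1". The criteria in Sections 8.2.1 and 8.2.2 contain no waiting time.
- Section 14.2.1, in the timeline to the final analysis: "randomization will take place 9 months after registration of the last patient".
- Section 14.4: "For randomized patients, the QoL after the last induction chemotherapy will then be considered as baseline". Section 10.4 schedules that questionnaire "after cycle 9 or earlier in case of premature discontinuation of induction treatment"; the next one is 6 months after the start of maintenance.
- Appendix I equates the blood sample taken before maintenance with the one taken after the last induction cycle.

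**The concern.** Both sentences are current text, both count from the start of the last induction cycle, and both govern the start of maintenance. One sets a lower limit of 12 weeks and the other an upper limit of 12 weeks.

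This is a conduct rule for every randomised patient. A site that follows Section 8.2 leaves patients without treatment after induction, although the protocol neither describes nor justifies a treatment-free period, and it breaches Section 9.2.1 on every day but one. PFS runs from randomisation (Section 13.1), so sites that follow different sections would place time zero at different distances from the end of induction. The quality-of-life baseline would also be older at the first maintenance dose.

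**Working it through.** **Inputs.** Nine induction cycles of 28 days, with ixazomib on days 1, 8 and 15 and "a daily dose of thalidomide (100 mg) continuously plus dexamethasone (40 mg) on days 1, 8, 15 and 22" (Section 9.1.1); a minimum of six cycles in defined cases (Section 8.2.1); induction starting within 4 weeks of registration (Section 9.1.1); 9 months from registration to randomisation (Section 14.2.1). Assumptions: no cycle delays, evaluation and questionnaire at the end of the last cycle, and 30.44 days per month.

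**Overlap of the two rules.** Let t be the time from the start of the last induction cycle to the start of maintenance. Section 8.2 requires t ≥ 12 weeks and Section 9.2.1 requires t ≤ 12 weeks. Only t = 12 weeks meets both.

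**Nine-cycle patient.** The last cycle starts at 8 × 4 = week 32 and ends at week 36. Twelve weeks after its start is 32 + 12 = week 44.

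- Week 36 = 36 × 7 / 30.44 = 8.3 months
- Week 44 = 44 × 7 / 30.44 = 10.1 months
- Planned 9 months = 9 × 30.44 / 7 = 39.1 weeks

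Months from registration to the start of maintenance:

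| | Section 9.2.1 | Section 8.2 |
|---|---|---|
| Induction starts at registration | 8.3 to 10.1 | 10.1 or later |
| Induction starts 4 weeks after registration | 9.2 to 11.0 | 11.0 or later |

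The second row adds 4 weeks: 40 × 7 / 30.44 = 9.2 and 48 × 7 / 30.44 = 11.0. The planned 9 months lies inside the Section 9.2.1 window in the first row and just before it in the second. It is 1.1 to 2.0 months short of the Section 8.2 minimum.

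**Six-cycle patient.** The last cycle runs from 5 × 4 = week 20 to week 24. Week 20 + 12 = 32 (32 × 7 / 30.44 = 7.4 months) is the latest start under Section 9.2.1 and the earliest under Section 8.2.

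**Treatment gap under Section 8.2.** Twelve weeks after day 1 of the last cycle is day 85. The untreated time after the 28-day cycle is 12 − 4 = 8 weeks (days 29 to 84, 56 days). Minimum intervals from the last induction dose to the first maintenance dose:

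- Ixazomib: 85 − 15 = 70 days (29 − 15 = 14 between cycles on schedule)
- Dexamethasone: 85 − 22 = 63 days (29 − 22 = 7 on schedule)
- Thalidomide: 85 − 28 = 57 days (daily on schedule)

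Dexamethasone and thalidomide are not part of maintenance, so the ixazomib interval is the one that matters for the active arm. For scale, Section 9.1.2 ends induction treatment if a toxicity delay exceeds 6 weeks.

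**Quality-of-life baseline.** Its age at the first maintenance dose is 0 to 8 weeks under Section 9.2.1 and at least 8 weeks under Section 8.2, with no questionnaire scheduled in between.

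**Timeline.** The plan's own figure is 18 + 9 + 12 = 39 months. With the Section 8.2 minimum it becomes at least 18 + 10.1 + 12 = 40.1 months, or 18 + 11.0 + 12 = 41.0 months if induction starts 4 weeks after registration.

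**The case against.** The conflict itself is hard to dispute; the case on the other side is that it matters little.

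- **Nothing in the primary analysis changes.** This stands. The PFS definition, the test, the 55 events and the 94 randomised patients are the same under either section, and randomisation stratified by center (Section 15.2.2) keeps the arms comparable even if sites differ.
- **Section 9.2.1 already allows a gap of up to 8 weeks.** This also stands: time zero and the age of the quality-of-life baseline can vary within that range after the correction. What Section 8.2 adds is to turn the longest permitted gap into the shortest, with no upper limit. Section 14.4 also describes the quality-of-life analysis as mainly descriptive and of limited power.
- **The timeline effect is small.** The 40.1 months equals the latest case under Section 9.2.1, the 4-week lag behind 41.0 months applies under either section, and the 39-month projection is conditional on 55 events. The timeline helps to show which sentence is wrong, but it is not a material harm.
- **Some of the evidence against Section 8.2 shows only order.** This is fair for Section 7, Section 14.4 and Appendix I, none of which fixes an interval. The absence of a waiting time in the criteria is an argument from silence, and the 9 months is a rounded figure that equals the synopsis duration of induction. The sequence in Section 9.2.1 and, more loosely, the 9-month plan carry the argument.
- **Status is refreshed before maintenance.** Section 10.1 requires blood and urine values within 4 weeks before the start, and eligibility is checked at randomisation. This limits the risk from outdated values, but it does not tell a site when to treat.

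Many sites would probably guess the intended meaning. A rule on when to randomise and treat should not depend on that.

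**Conclusion.** Section 8.2 is wrong as written and should be fixed. The two rules agree only at exactly 12 weeks, and the rest of the protocol fits the upper limit better than the lower one. Followed literally, Section 8.2 imposes at least 8 untreated weeks after the last induction cycle, against 0 to 8 weeks under Section 9.2.1, and at least 70 days between ixazomib doses for patients in the active arm. It also delays a nine-cycle patient to week 44 or later, where Section 14.2.1 plans for about week 39. These figures assume 28-day cycles without delay. The contradiction does not depend on that assumption. The issue concerns conduct and consistency between sites, not the validity of the primary comparison.

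**What to change.** In Section 8.2, replace *at least 12 weeks* with *within a maximum of 12 weeks*. Sections 8.2 and 9.2.1 then set the same limit. Because Section 9.2.1 places randomisation before the first maintenance dose, that limit covers both. The 39-month timeline, the 55 events and the 94 randomised patients stay as they are. The cost is a wording correction in one sentence, with no extra patients, procedures or recalculation.
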